8.2 Disposition of Study Subjects

Subject disposition will be summarized in total, by surgical population (pediatric and adult), surgical procedure group, and procedure subgroups using counts and percentages. The number and percentage of subjects in the AES who failed screening, completed the study and discontinued from the the study will be tabulated along with the specific reasons for discontinuation.

8.3 Demographic, Baseline, and Surgical Characteristics

Summary statistics of subject demographics (age, gender, ethnicity, race and childbearing potential if female) and vital signs (height, weight, and body mass index) will be presented in total, and by surgical population (pediatric and adult), surgical procedure group, and procedure subgroups. Listings will be presented for subject's inclusion/exclusion criteria, demographic, vital sign, and background information.

Background information for pediatric general surgical procedure, and for hepatopancreatobiliary, lower GI, gastric, gynecological, urological, and thoracic adult procedures will be summarized separately. A listing will be provided for background information of each procedure group.

Medical history will be summarized by Medical Dictionary for Regulatory Activities (MedDRA) system organ class and preferred term in total, and by surgical population (pediatric and adult), surgical procedure group, and procedure subgroups. A listing will be presented for medical history. Prior and concomitant medications, surgical history and concomitant procedures will be provided in listing only.

Surgical characteristics including, at minimum, estimated blood loss, requirement for blood transfusion, and procedure duration will be summarized by surgical population (pediatric and adult), surgical procedure group, and procedure subgroups and in total

8.4 Primary and Secondary Endpoints and Associated Hypotheses

The study endpoints are representative of endpoints that are currently reported in the available literature for similar energy devices, and this will allow for comparisons with the results from this study.

8.4.1 Primary Endpoint and Associated Hypotheses

The primary performance endpoint in this study is the number and percentage of vessels where hemostasis (\leq Grade 3) is achieved using the HARMONIC 1100 Shears device. The hemostasis grading scale which was adapted from Siegel et al.² is defined as:

- Grade 1: no bleeding at transection site;
- Grade 2: minor bleeding at transection site, no intervention needed;
- Grade 3: minor bleeding at transection site, mild intervention needed, use of compression, basic energy devices (monopolar and/or bipolar device), and/or touch-

ups with HARMONIC 1100 Shears; or

- Grade 4: significant bleeding (e.g., pulsatile blood flow, venous pooling) requiring intervention such as extensive coagulation or use of additional hemostatic measures (e.g., hemoclips, staples, sutures, fibrin sealants, other advanced energy products).

The following hypothesis will be evaluated for the primary performance endpoint:

$$H_0: p \leq 87.5\%$$

$$H_1: p > 87.5\%$$

Where p is the percentage of transections achieving a Grade 3 or lower hemostasis rating and 87.5% is set as a performance goal for the lower bound of acceptable hemostasis. A two-sided 95% confidence interval will be calculated for p based on the sample proportion of transections where Grade 3 or lower hemostasis was achieved using exact Binomial methods proposed by Clopper-Pearson and the lower limit of this confidence interval will be compared to 87.5% to evaluate the above hypotheses. A p-value will be determined based on an exact binomial test. The null hypothesis will be rejected if the lower limit of the confidence interval is greater than 87.5%.

The hypothesis and evaluation of hypothesis for the secondary performance endpoint for the proportion of vessels transected of diameter size $> 5-7$ mm with hemostasis grade 3 or lower will be similar to the primary performance endpoint as described above.

The primary and secondary performance endpoint will be summarized at the vessel transection level as multiple vessel transections per subject are expected; that is, the denominator for the primary endpoint will be the total number of vessel transections and the numerator will be the number of vessel transections where hemostasis (\leq Grade 3) is achieved. The number and percentage of vessels where hemostasis is achieved will be summarized and an exact two-sided 95% confidence interval will be estimated for each surgical population (pediatric and adult), surgical procedure group, procedure subgroup, the > 5 to 7 mm diameter vessel population, and in total.

8.4.2 Secondary Endpoints and Associated Hypotheses

No formal hypotheses are specified for the secondary endpoints of this study.

Counts and percentages will be provided for the following secondary endpoints:

- Categories of 5-point scale (very dissatisfied, dissatisfied, neither satisfied or dissatisfied, satisfied, or very satisfied) for sealing and transection of lymphatic vessels completed by the HARMONIC 1100 Shears device:
- Categories of hemostasis grading scale (1-4) for all vessel transected
- Type, name, and number of additional hemostasis measures required to achieve hemostasis for Grade 4 vessel transections

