2.2 SECONDARY PERFORMANCE ENDPOINTS

The secondary performance endpoints will be:

- Distribution of 5-point scale scores for sealing and transection of lymphatic vessels completed by the HARMOINC 1100 Shears. The scale will be a 5-point scale (very dissatisfied, dissatisfied, neither satisfied or dissatisfied, satisfied, or very satisfied) asking how satisfied the surgeon was with the use of the device for the task;
- Distribution of hemostasis grading scale (1-4) for each vessel transected; and
- Type, name, and number of additional hemostasis measures required to achieve hemostasis for Grade 4 vessel transections.

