5.9.4 Primary and Secondary Endpoint Analyses

The number and percentage of vessels where hemostasis is achieved (≤ Grade 3) will be summarized and an exact two-sided 95% confidence interval based on Clopper-Pearson's method will be estimated for each surgical population (pediatric and adult), surgical procedure group, procedure subgroup, the > 5 to 7 mm diameter vessel population, and in total. The performance goal hypothesis will be tested as described in Section 5.4 on the total population and the > 5 to 7 mm diameter vessel population.

Summary statistics appropriated for categorical or continuous variable will be provided for type, size, and number of vessels transected, as well as for the grading scale distribution for all vessels transected, number of times HARMONIC 1100 Shears touch-ups were required, incidence of requirement for additional measures to obtain hemostasis on vessels (other advanced energy devices or hemostatic measures), and 5-point scale scores for sealing and transection of lymphatic vessels completed by the HARMONIC 1100 Shears. In addition, these analyses will also be completed for the vessels in the > 5 to 7 mm diameter size vessel range.

All device-related and procedure-related AEs reported during the study will be coded to MedDRA. All AEs will be summarized by MedDRA system organ class and preferred term by surgical population (pediatric and adult), surgical procedure group, procedure subgroup, and in total. Separate summaries will be provided for device-related and procedure-related AEs. Serious AEs will be summarized in a similar manner. In addition, these analyses will also be completed for the vessels in the > 5 to 7 mm diameter size vessel range.

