Interval windows for the purpose of analysis in this study will not be defined outside of those already specified in the protocol for visit scheduling as the collection of data for the primary and secondary performance endpoints occurs intra-operatively. The final visit occurs approximately 4 weeks after surgery, thus no interval windows need to be defined given the absence of long-term follow-up in this study. The Schedule of Events specifies a window of 14 days around the scheduling of the 4-week follow-up visit, and any information entered in the eCRFs at this visit will correspond to the 4-week visit. There will be no assigning of observations to time points outside of the visit to which they are recorded in the eCRFs.

5 Levels of Significance

The hypotheses in this study will be evaluated using a one-sided significance level of 0.025. Estimation of all additional endpoints will be performed using two-sided 95% confidence intervals.

6 Analysis Sets

All Enrolled Set (AES): The all enrollment set contains all subjects who provide informed consent for this study . The AES will be used for subject disposition and all listings.

Full Analysis Set (FAS): The FAS will includeds all subjects in whom the HARMONIC 1100 Shears is utilized during the surgical procedure to transect at least one vessel and have assessment for the primary endpoint. The summary of all primary and secondary performance and safety endpoints will be performed by surgical population (pediatric and adult), surgical procedure group, procedure subgroup, and on the entire pooled set of subjects. The hypotheses described in Section 8.4.1 below will be evaluated on the pooled set of subjects and the > 5 to 7

mm diameter vessel population. The > 5 to 7 mm diameter vessel population will be based off the surgeon determination of the vessel size.

Safety Analysis Set (SAS): The SAS will include all subjects who signed informed consent and for whom HARMONIC 1100 Shears device is utilized during the surgical procedure. The safety endpoints will be summarized using SAS by surgical population (pediatric and adult), surgical procedure group, procedure subgroup, and on the entire pooled set of subjects.

7 Sample Size Justification

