Primary performance analysis: A sample size of at least 165 subjects is required to have a minimum of 80% power for rejecting the null hypothesis that the rate of Grade 3 or lower transections is less than or equal to 87.5% when the expected rate of Grade 3 hemostatic transection is at least 94.0% using exact binomial test and a one-sided significance level of 0.025. This sample size estimation makes the assumption of one transection per subject which is likely very conservative as most subjects may have 2 or more transections during their procedure. Therefore, it is expected that greater than 165 transections will be observed and thus the study will be well powered for evaluating the performance goal hypothesis under the assumption of independence of observations. At the time of the study protocol amendment 3, it was found that on average there were 2 vessel transections per subject.

The assumption of independence and its impact on the overall study conclusion will be evaluated through sensitivity analyses. Given that the primary endpoint is being evaluated intra-operatively, it is not anticipated that there will be subject dropout prior to evaluating this endpoint, thus no adjustment or increase in subject enrollment is planned to account for dropout. A minimum of 33 subjects will be enrolled into each of the five individual procedure subgroups.

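### SAP 8.4.2 denies that any secondary endpoint has a formal hypothesis although the >5 to 7 mm test is defined and powered elsewhere, and no testing order links that test to the primary

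*SAP*

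**What the plan says.** **Text that defines a formal large-vessel test.** SAP 8.4.1 sets the primary hypothesis, in which "87.5% is set as a performance goal for the lower bound of acceptable hemostasis". It then turns to large vessels: "The hypothesis and evaluation of hypothesis for the secondary performance endpoint for the proportion of vessels transected of diameter size" >5 to 7 mm is to follow the same pattern as the primary. SAP 6 states: "The hypotheses described in Section 8.4.1 below will be evaluated on the pooled set of subjects and the > 5 to 7" mm vessels. SAP 7 gives this test its own sample size, at least 165 vessels for 80% power. Protocol 5.4, 5.6 and 5.7 agree, and protocol 5.9.4 tests the performance goal "on the total population and the > 5 to 7 mm diameter vessel population".

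**Text that points the other way.** SAP 8.4.2, the section on secondary endpoints and their hypotheses, opens with "No formal hypotheses are specified for the secondary endpoints of this study". It then lists three descriptive endpoints: lymphatic satisfaction scores, the distribution of hemostasis grades, and the additional measures used for Grade 4 transections. Protocol 2.2 introduces the same three with "The secondary performance endpoints will be". The >5 to 7 mm rate is on neither list, although it is the subject of the secondary objective.

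**Significance level.** SAP 5: "The hypotheses in this study will be evaluated using a one-sided significance level of 0.025". The plural covers both tests. Neither document gives a sequence, a gate, a split of alpha or an overall error rate.

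**The concern.** The large-vessel test is a substantial part of the study. The 165-vessel count is a stated enrollment goal, and the protocol synopsis ties the procedure-group maxima to meeting the secondary endpoint. Yet someone working from SAP 8.4.2 or protocol 2.2 would report the result as descriptive, while someone working from SAP 8.4.1 would report a confirmed or failed hypothesis.

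The second gap is the order of testing. Two tests at one-sided 0.025 each, with nothing linking them, leave open whether a >5 to 7 mm claim may stand after the primary has failed. If it may, the probability of at least one false rejection is higher than for either test alone. If that choice is left until results are known, it can be influenced by them.

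**Working it through.** **Inputs.** Null rate 87.5% (SAP 8.4.1). Design rate 94.0% with an exact test (SAP 7: "when the expected rate of Grade 3 hemostatic transection is at least 94.0% using exact binomial test"). One-sided 0.025 (SAP 5). Large-vessel target 165 (SAP 7). About 2 transections per subject (SAP 7) and 165 to 328 subjects (SAP 1.2), so total vessels run from 165 × 2 = 330 to 328 × 2 = 656.

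**Step 1: reproduce the plan's sample size.** Take the smallest r with P(X ≥ r | n = 165, p = 0.875) ≤ 0.025. This gives r = 153.

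- Attained size: P(X ≥ 153 | 0.875) = 0.0221.
- Power: P(X ≥ 153 | 0.94) = 0.807.
- The Clopper-Pearson lower limit is 87.64% at 153/165 and 86.90% at 152/165, so the interval rule and the exact test agree.

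The stated 165 and 80% are confirmed.

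**Step 2: error rate with no testing order.** Let A be the number of successes among the 165 large vessels and B the number among the other N − 165, independent, all with true rate 87.5%. The primary rejects if A + B ≥ r(N). The large-vessel test rejects if A ≥ 153. Then

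P(both) = Σ over a = 153 to 165 of P(A = a) × P(B ≥ r(N) − a)

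P(at least one) = P(primary) + P(large-vessel) − P(both)

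| Total vessels N | r(N) | P(primary) | P(large-vessel) | P(both) | P(at least one) |
|---|---|---|---|---|---|
| 330 | 301 | 2.14% | 2.21% | 0.69% | 3.67% |
| 400 | 364 | 1.74% | 2.21% | 0.49% | 3.46% |
| 500 | 453 | 1.84% | 2.21% | 0.41% | 3.64% |
| 656 | 591 | 2.31% | 2.21% | 0.38% | 4.14% |

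At 656, for example, 2.31 + 2.21 − 0.38 = 4.14. At 330 the rounded entries sum to 3.66; the unrounded sum is 3.67. Because critical values are whole numbers, other totals fall slightly either side of this pattern.

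The part a gate would remove is P(large-vessel) − P(both): 2.21 − 0.69 = 1.5% at 330 and 2.21 − 0.38 = 1.8% at 656.

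The limits are 2.21% if every vessel were >5 to 7 mm (the same test twice) and 1 − 0.975² = 4.94% if two tests of exactly 0.025 were independent. If only one null is true, the false-rejection probability is at most 2.5%.

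**Step 3: fixed sequence, primary first.** When both nulls hold, a false rejection requires the primary to reject, so the probability is the P(primary) column, 1.7% to 2.3%. When only the large-vessel null holds, it is at most 2.21%. At a true rate of 94% and N = 330, the primary has 98.4% power. Large-vessel power is 80.7% ungated, and P(both) is 80.5%.

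**Step 4: alternative, equal split at 0.0125 each.** With 165 large vessels r = 154 and power falls to 71.2%; the smallest vessel count that reaches 80% is 195. The fixed sequence needs no extra vessels.

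**The case against.** The strongest reply is that nothing here is misstated. The 8.4.2 sentence introduces three descriptive endpoints and can be read as covering only those, while the large-vessel test is described consistently in every other relevant section of both documents. The endpoints are labelled primary and secondary, which suggests a hierarchy, and under a hierarchy nothing is inflated. The only sentence about evaluating success, in SAP 8.8, concerns the primary endpoint.

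Much of this stands. A reader might infer that the plan breaches a stated 2.5% overall error rate. The documents do not support that: SAP 5 and protocol 5.5 set the level at which the hypotheses are evaluated and promise nothing across them. A reader might also infer that the primary test is inflated by the second test. It is not; on its own, and under independence, its size is 1.7% to 2.3% in the scenarios above. At the design rate the order seldom matters: with 94% throughout and 330 vessels, large-vessel success with primary failure has probability of about 0.2%. It would matter more if smaller vessels performed worse.

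What does not stand is that the text needs no repair. The 8.4.2 sentence is unqualified and refers to the whole study, and the section before it uses the word secondary for the tested endpoint. The hierarchy suggested by the labels is never written down.

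**Conclusion.** The contradiction between SAP 8.4.2 and SAP 6, 7 and 8.4.1 is plain on the text and needs no assumption. The multiplicity point is conditional: because no order is stated, the chance of at least one false rejection can reach about 3.5% to 4.1%. That requires both true rates to be 87.5% and a large-vessel claim to be allowed after a failed primary.

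These figures assume exactly 165 large vessels, two transections per subject and independent vessels. Correlation within subjects would change them, in a direction not worked out here. They also use the exact test alone. SAP 8.8 lets a mixed model replace the exact result for the primary when the two disagree, so neither the ungated range nor the gated 1.7% to 2.3% is the error rate of the full decision rule. The point is worth correcting because it affects a formally powered claim and the repair costs almost nothing.

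**What to change.** Two changes to the SAP, made before database lock:

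1. In 8.4.2, limit the opening sentence to the three endpoints listed there, and say that the >5 to 7 mm hypothesis is covered in 8.4.1.
2. In 8.4.1, state that the >5 to 7 mm hypothesis is tested at one-sided 0.025 only if the primary null has been rejected, and name the analysis that decides this. Since SAP 8.8 can override the exact result with the mixed model, the gate should follow whichever analysis determines primary success.

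The cost is a loss of about 0.2 percentage points of large-vessel power (80.7% to 80.5% at 330 vessels and a true rate of 94%) and no confirmatory large-vessel claim if the primary fails. Sample size and the primary alpha are unchanged.

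Adding the endpoint to protocol 2.2 and the synopsis would tidy the lists, but it would be a protocol amendment with its own approvals. Protocol 5.4, 5.6, 5.7 and 5.9.4 already specify the test, so this is optional and can wait for any later amendment.

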8.4.3 Summary of additional key data

Summary statistics will be provided for the following endpoints:

- Procedure duration
- Use of any other energy device (monopolar, traditional bipolar, advanced bipolar, ultrasonic) in primary procedure (type, name, and number of device and reason for use), if applicable
- Surgeon questionnaire administered once per investigator
- Generator questionnaire after each procedure for each GEN11 used
- Surgical procedure conducted
- Hospital stay duration
- Name and number of vessels that were transected, surgeon determination of diameter size range (< 3 mm, 3 to 5 mm, and > 5 to 7 mm)
- Occurrence and location of cancer and occurrence of pre-surgical radiation/chemotherapy within 90 days prior to surgery, if applicable
- Occurrence of vessel skeletonization
- Presence of inflamed tissue, calcified tissues/vessels, atherosclerotic tissue, fibrotic tissue, or presence of adhesions intraoperatively
- Volume of estimated intra-operative blood loss
- Occurrence of blood transfusion, total required units of blood, and time point of transfusion
- Type of additional mild interventions (use of compression, monopolar, bipolar devices, and/or touch-ups with HARMONIC 1100 Shears) required to achieve hemostasis for Grade 3 vessel transections including number of times when HARMONIC 1100 Shears touch-ups were used
- Procedure-related AEs (Possible, probable or casual) and
- Protocol deviation classified as minor or major, rationale for deviation, type of protocol deviation, and outcome of protocol deviation in terms of subject's discontinuation of study

8.5 Safety Analyses

The primary safety endpoint in this study is the occurrence of device-related AEs. As per the study protocol, device-related AEs are those identified as having a relationship of possibly, probably, or causally. AEs unrelated to the study device are recorded as 'not related' on the CRF. Both device-related and procedure-related AEs reported during the study will be coded to MedDRA. All reported AEs will be summarized by MedDRA system organ class and preferred term by surgical population (pediatric and adult), surgical procedure group, procedure subgroup, and in total. Separate summaries will be provided for device-related and procedure-related AEs. Serious AEs will be summarized in a similar manner. In addition, these analyses will also be completed for the vessels in the > 5 to 7 mm diameter size vessel range.

Safety endpoints are as follows:

- All AEs
- All Serious AEs
- All AEs related to the study device
- Serious AEs related to the study device
- All AEs related to the study procedure
- Serious AEs related to the study procedure

Additional key safety outcomes identified in the CER #SCN070380 (ref. Table 40) that includes the bleeding/hemorrhaging and infection (including abscess) will be presented by surgical population (pediatric and adult), surgical procedure group, procedure subgroup, and in total. The observed event rates for these key safety outcomes from the current study will be presented along with the median and range event rates from the CER for descriptive comparison with no statistical test performed.

8.6 Plans for Interim Analysis

No interim analyses are planned for this study.

8.7 Handling of Missing Data

All summaries will be performed only on subjects undergoing the scheduled procedure and only observed data will be summarized. There will be no imputation of data for early terminated subjects or for missing data within the database.

8.8 Sensitivity Analyses

The analysis of the primary performance endpoint described above in Section 8.4.1 makes the assumption of independence of transactions within a subject in estimation of variance for the confidence interval calculation. To account for the potential correlation among transactions within a subject, a sensitivity analysis will be performed where the 95% confidence interval will be estimated using a generalized linear mixed model. The underlying distribution of the dependent variable in the model is logistic as the outcome variable is binary (i.e., hemostasis achieved or not achieved). A random intercept term at subject-level will be used in the generalized linear mixed model to account for the within subject correlation in achieving hemostasis. The distribution of the random intercept model is assumed to be Gaussian. If the inference from the mixed model is not consistent with the inference from the primary endpoint analysis as described in Section 8.4.1 then the inference from the mixed model will be used to evaluate success.

Example SAS code:

*create a pseudo variable group so that the 95% CI for intercept can be estimated:

```
data dat2;
  set dat1;
  group = "pseudo";
run;
```

```
pro glimmix data= dat2;
class id group;
model outcome(Event ="0") = group / s dist=binary link=logit;
random intercept /subject = id;
lsmeans group/ cl ilink ; * The results of interest (95% CI of the rate of hemostasis) are
presented on the last two columns;
run;
```

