5.7 SAMPLE SIZE JUSTIFICATION

Primary performance analysis: A sample size of at least 165 subjects is required to have a minimum of 80% power for rejecting the null hypothesis that the rate of Grade 3 or lower transections is less than or equal to 87.5% when the expected rate of Grade 3 hemostatic transections is at least 94.0% using an exact binomial test and an one-sided significance level of 0.025. This sample size estimation makes the assumption of one transection per subject which is likely very conservative as most subjects may have 2 or more transections during their procedure. Therefore, it is expected that greater than 165 transections will be observed and thus the study will be well powered for evaluating the performance goal hypothesis under the assumption of independence of observations. At the time of study protocol amendment 3 it was found that on average there were 2 vessel transections per subject.

Study Number: ENG_2020_06 Version: Amendment 3

The assumption of independence and its impact on the overall study conclusion will be evaluated through sensitivity analyses. Given that the primary endpoint is being evaluated intra-operatively, it is not anticipated that there will be subject dropout prior to evaluating this endpoint, thus no adjustment or increase in subject enrollment is planned to account for dropout. A minimum of 33 subjects will be enrolled into each of the five individual procedure subgroups.

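### SAP 8.8 lets a mixed-model interval for a different rate decide success, so a failed Clopper-Pearson test can become a success when failures cluster within subjects

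*SAP*

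**What the plan says.** SAP 8.4.1 defines p as the percentage of transections rated Grade 3 or lower; "the denominator for the primary endpoint will be the total number of vessel transections". The decision rule there, and in Protocol 5.4, is: "The null hypothesis will be rejected if the lower limit of the confidence interval is greater than 87.5" percent, with the limit taken from the two-sided 95% Clopper-Pearson interval. SAP Section 7 states the power for this test, "using exact binomial test and a one-sided significance level of 0.025".

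Protocol 5.4 promises a sensitivity analysis for correlation between transections in the same subject and leaves its details to the SAP. Protocol 5.7 says: "The assumption of independence and its impact on the overall study conclusion will be evaluated through sensitivity analyses".

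SAP 8.8 supplies the analysis: a logistic mixed model with a Gaussian random intercept per subject. The example code calls the procedure as "pro glimmix data= dat2", without a METHOD option, and takes the interval from "lsmeans group/ cl ilink". If the mixed model and the 8.4.1 analysis are not consistent, "then the inference from the mixed model will be used to evaluate success".

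**The concern.** **The override.** If the two analyses agree, the outcome is the mixed model's. If they disagree, the mixed model decides. So it decides in every case, while the stated alpha and power belong to the exact test.

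**The target.** The p in H0 is a marginal rate over all transections. LSMEANS with ILINK returns expit(intercept), the rate for a subject whose random intercept is zero. With a rate above 50% and any between-subject variation, that value exceeds p. An analysis meant to guard against correlation can therefore favour success more as correlation grows.

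**The method.** The SAP names no estimation method. As a matter of software behaviour (not stated in the documents), omitting METHOD gives residual pseudo-likelihood. Quadrature maximum likelihood fits the same described model and is not excluded. The two can give very different limits.

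At stake is whether the primary endpoint is declared met.

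**Working it through.** **1. The plan's own figure.** With n = 165, p0 = 87.5%, p1 = 94.0% and one-sided 0.025, the exact test needs 153 successes. Its exact alpha is 2.21% and its power 80.7%. The stated minimum of 80% reproduces. With 330 independent transections, 301 successes are needed and power is 98.4%.

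**2. What ILINK targets when H0 is true.** Solve E[expit(b + σZ)] = 0.875 for b, with Z standard normal, and report expit(b). The documents give no within-subject correlation, so σ is assumed.

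| σ | ICC | expit(b) |
|---|---|---|
| 0.5 | 0.03 | 88.5% |
| 1 | 0.11 | 90.8% |
| 1.5 | 0.21 | 93.3% |
| 2 | 0.31 | 95.5% |

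Every value exceeds the 87.5% goal although p equals it.

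**3. Worked data.** Take 165 subjects with 2 transections each (2 is the documented average) and 300/330 = 90.9% controlled. The Clopper-Pearson lower limit is 87.28%, a fail; 301/330 gives 87.62%. The total stays at 300 while the pattern of failures changes.

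| Subjects failing both / one / none | Pseudo-likelihood lower limit | Clustered lower limit |
|---|---|---|
| 5 / 20 / 140 | 87.63% (success) | 86.7% (fail) |
| 10 / 10 / 145 | 88.9% (success) | 86.0% (fail) |

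Quadrature gives 90.0% for the first row.

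Clustered limit, first row: the squared subject residuals sum to 140(0.1818²) + 20(0.8182²) + 5(1.8182²) = 34.55. The variance is (165/164) × 34.55/330² = 0.000319, so SE = 0.01787. On the logit scale, SE = 0.01787/(0.9091 × 0.0909) = 0.216. The limit is expit(2.3026 − 1.9745 × 0.216) = 86.7%.

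Stronger clustering lowers the clustered limit, as it should, and raises the mixed-model limit.

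**4. False success at a true p of 87.5%.** Two transections per subject, enumerated exactly over the numbers of subjects with 0, 1 or 2 controlled transections. Entries are for σ = 1 / 1.5 / 2.

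| Rule | 165 subjects | 328 subjects |
|---|---|---|
| Clopper-Pearson alone | 2.7 / 3.3 / 3.8% | 2.9 / 3.5 / 4.1% |
| SAP 8.8, pseudo-likelihood | 2.8 / 3.7 / 5.4% | 3.1 / 4.9 / 7.9% |
| SAP 8.8, quadrature | 6.2 / 23.9 / 55.3% | 18.7 / 64.7 / 94.6% |
| Clustered interval | 2.0 / 2.2 / 2.3% | 2.3 / 2.3 / 2.3% |

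At σ = 0 every method lies between 1.3 and 2.5%.

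Variable counts with mean 2 (1 + Poisson(1), or geometric; 4,000 simulated trials per setting, Monte Carlo SE about 0.2 to 0.8 points) widen the ranges. Over both count patterns and the fixed design, for σ from 1 to 2:
- Pseudo-likelihood: 2.8 to 7.6% at 165 subjects and 3.1 to 13.2% at 328.
- Clopper-Pearson alone: 2.7 to 5.5% and 2.7 to 6.2%.
- Added by the override under the printed code: 0.1 to 2.2 points and 0.3 to 7.0 points.
- Clustered interval: 1.8 to 3.0% overall.

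**5. The other direction.** Quadrature can also withdraw a sound success. At a true 94% with no correlation (165 × 2), success falls from 98.4% by Clopper-Pearson to 74.3%.

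**The case against.** The strongest reply concerns size:

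- **Weak correlation.** Under the printed code little happens. At 165 subjects with two transections each, the override adds 0.01 points at σ = 0.5, 0.09 at σ = 1, 0.49 at 1.5 and 1.55 at 2. Part of the excess over 2.5% is Clopper-Pearson's own independence problem, which both documents acknowledge.
- **Unprinted method.** The very large error rates come from quadrature, which the SAP does not print.
- **Chosen examples.** The example data are one success short of passing and clearly clustered. Independence would give about 165 × (1/11)² = 1.4 double failures, not 5. The within-subject correlation is about 0.27 in the first data set and 0.63 in the second. With the same total and only 3 or 4 double failures, the pseudo-likelihood limit is 87.30% or 87.44%, still a fail.
- **Planning rate.** At a true 94% (165 × 2, σ from 0.5 to 2) success is 97.2 to 98.3% by Clopper-Pearson and 97.6 to 98.3% by the printed code.
- **Delegation.** Protocol 5.4 left the details to the SAP, and the SAP fixed them in advance.

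The points on size stand, and the figures above reflect them. They do not remove the defect. The rule still compares the wrong quantity with 87.5%, and the error grows with the correlation it is meant to handle. Code headed as an example does not bind the estimation method. Delegating the details of a sensitivity analysis is not the same as letting it replace a failed primary test.

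**Conclusion.** The concern holds. From the text alone, the mixed model always decides success, and its interval is not for the p of H0. That a failed exact test can become a success is shown with explicit data under the printed code.

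The practical size rests on two things the documents leave open: the within-subject correlation, assumed here as σ up to 2 (ICC up to 0.31), and the estimation method. With no correlation there is no inflation. With pseudo-likelihood the extra false success is slight at ICC 0.11 and reaches 2.2 points at 165 subjects, or 7.0 points at the maximum enrolment of 328. With quadrature it is already material at ICC 0.11. Because the rule settles the primary endpoint, it must be corrected before database lock.

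**What to change.** In SAP 8.8:

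1. Replace the ILINK interval with a subject-clustered interval for the overall transection rate, for example GEE with independence working correlation and a small-sample-corrected sandwich variance. If the mixed model is kept, integrate over the random intercept and report the marginal rate with its interval.
2. Reword the override: the cluster-adjusted result may withhold success, but it may not turn a failed Clopper-Pearson test into a success.
3. Name the estimation method.
4. Define the outcome code. The example models Event = 0, so the interval is for hemostasis achieved only if 0 means achieved.

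The cost is SAP wording and a few lines of code, with no extra subjects. The chance of success falls slightly if correlation is real. At a true 94% with 165 × 2 and σ = 1 / 1.5 / 2, it goes from 98.1 / 97.7 / 97.2% (Clopper-Pearson alone) to 97.1 / 96.0 / 94.5% (both required).
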